## 1. Protocol Summary

**Title of study:** Low fresh gas flow during elective general anaesthesia -  
A study comparing the Flow-I and a conventional anaesthetic machine with a circle system including a bellow reservoir.

**Institution:** Department of Anaesthesia & Intensive Care Danderyds University Hospital, Institution for Clinical Science, Karolinska Institutet, Stockholm, SWEDEN

**Study time-lines:** Patients inclusion in 8 month, study report in 12 month, from initiation of patient into study.

**Objective:** To test the hypothesis that the Flow I patient circle and fresh gas generation provides a faster and less gas consuming equilibrium and maintenance of general anaesthesia as compared to a conventional anaesthetic machine including a breathing circle with a below reservoir.

The study will compare Flow I to a conventional anaesthetic machine during routine elective general surgery in ASA 1-2 patients under general anaesthesia based on desflurane at a fresh gas flow of 1 L/min.

**Study design:** prospective, randomized study.

**Participants:** one hundred ASA 1-2 patients aged 20 – 60 years scheduled for elective general anaesthesia will be recruited. Patients will be randomized to Flow I or a conventional anaesthetic machine having general desflurane anaesthesia at a fresh gas flow of 1 l/min fresh gas flow.

**Duration of treatment:** Study protocol covers 72 hours after end of anaesthesia (follow-up of quality of recovery until day 3) .

**Main measurements:**

Time to go from 1 to 1.5 MAC end-tidal concentration during controlled ventilation with a tidal volume of 6 ml/kg and a respiratory rate of 12 breaths per minutes.  
Amount anaesthesia agent consumed; Gram inhaled anaesthetic per minute anaesthesia.

## 2. Background

Desflurane, one of the third generation of inhaled halogenated anaesthetics has physiochemical properties promoting its use in low flow anaesthesia. The low blood and tissue solubility promotes its rapid equilibration and thus potential benefit when used in conjunction with lowering of the fresh gas flow. It has been shown superior to isoflurane for control of haemodynamic also at flow rates of 1 L/min.

Bennett et al compared desflurane and isoflurane for control of haemodynamic response. They found that Desflurane allowed for more rapid control of blood pressure response to surgical stimulus median 2 minutes (range 1 to 12 minutes) for desflurane versus 6 minutes (range 1 to 12 minutes,  $p = 0.011$ ). The desflurane group required fewer 30% incremental anaesthetic increases than the isoflurane group (1.8 versus 2.5,  $p = 0.016$ ) to control increased systolic blood pressure. End tidal/inspired drug concentration ratios were closer to unity in the desflurane patients both before (0.94 versus 0.80) and after (0.86 versus 0.70) changes in drug concentration to treat increased systolic blood pressure.

Avramov et al evaluated the effect of the fresh gas flow (FGF) rate and the anesthetic technique on the ability to control the acute hyperdynamic response to a specific surgical stimulus during surgery in 90 consenting ASA physical status I-III patients undergoing lower abdominal procedures. The patients were initially maintained with desflurane or isoflurane, 0.7 minimum alveolar anaesthetic concentrations, at total FGF rates of either 1 or 3 L/min. In response to the surgical stimulation of skin incision and retropubic dissection, an increase in mean arterial pressure (MAP) ~20% above the pre-incision baseline MAP value provoked a stepwise increase in the inspired concentration of the volatile anaesthetic or the IV administration of a variable-rate infusion of esmolol. They found that desflurane was significantly faster in controlling haemodynamic response to painful stimulation also at low, 1 L/min fresh gas flow. At 1 L/min, the average time to control the mean arterial pressure was significantly shorter with desflurane ( $17 \pm 12$  min) compared with isoflurane ( $29 \pm 16$  min), with 60% of the patients in the isoflurane group requiring rescue therapy.

Low blood gas solubility promotes in theory the use of the third generation inhaled anaesthetics for use during general anaesthesia with low fresh gas flow. The benefits of low blood and tissue solubility during low and minimal flow are not yet studied.

Reducing the fresh gas flow has many benefits, it reduces the risk for unnecessary work place contamination, it reduces the environmental pollution and it is cost-effective. Many institutions are therefore adopting low flow technique. Inhaled anaesthesia with low flow technique may also have benefits as compared to the intravenous anaesthetic technique, propofol based anaesthesia that has become increasingly popular. The low flow inhaled anaesthesia technique would assumingly become cost-effective also with the availability of generic low prize propofol. The easiness to start and continuously monitor end-tidal concentration should also be recognised.

Choi et al compared two fresh gas flows techniques and the time to effect: control of a blood pressure increase during surgery with sevoflurane. They compared the ability of the Zeus

multifunctional anaesthesia system to control haemodynamic response to surgical stimulation in semi-closed anaesthesia (SCA) or closed circuit anaesthesia (CCA) modes. Fifty patients undergoing gynaecological surgery were randomly assigned to SCA or CCA. Anaesthesia was induced with 2 mg/kg propofol and paralysis was achieved with 0.9 mg/kg rocuronium, i.v. and maintenance was with sevoflurane (minimum alveolar concentration [MAC], 1.0) using 2 l/min oxygen plus 2 l/min nitrous oxide (SCA 4 l/min group) or 50% oxygen plus 50% nitrous oxide (CCA group). An increase in mean arterial pressure (MAP) > 20% above baseline in response to surgical stimulation provoked a stepwise increase in sevoflurane (1.3 MAC and then 1.6 MAC), followed by fentanyl 1 µg/kg intravenously (rescue drug). The time required for MAP to return to within 10% of baseline was significantly shorter in the CCA group (6.4 +/- 3.6 min) compared with the SCA 4 l/min group (10.2 +/- 6.0 min). It seems reasonable to conclude that time to onset of effect of sevoflurane is rapid and dependent on the dose administered.

The breathing circle should ascertain an adequate gas mixture inhaled; oxygen and inhaled agent as well as absence of carbon dioxide. The anaesthetic machine provide the fresh gas entering the breathing circle. There are technical developments. The delivery of fresh gas differs between devices.

## **Objective**

To test the hypothesis that the Flow I breathing circle system without a below reservoir provides a faster and less anaesthetic vapour consuming wash-in and maintenance of  $E_{t_{\text{desflurane}}}$

The aim of the study is to compare gas kinetics, time needed in order to change the end-tidal concentration, and vapour consumption (and associated cost) between the novel Flow-I circle system and the standard anaesthesia equipment/machine at the centre (multi-centre study; 3 centres) during general anaesthesia for routine elective surgery in ASA 1-2 patients.

The study will compare The Flow I to a conventional anaesthetic machine including a breathing circle based on a below reservoir during routine desflurane with a fresh gas flow of 1 L/min in ASA 1-2 patients having elective surgery.

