#### **Exclusion criteria**

- COPD
- BMI > 30
- ASA >2
- Severe cardiovascular disease ASA >2
- Renal disease
- Diabetes
- Hepatic disease
- Psychiatric disease or any psychoactive medication

All patients will receive all treatment and care in accordance to the routines of the department apart from the volatile anaesthetic and fresh-gas flow that the patient is randomised to.

All study specific data will be recorded and collected on a Case Record Form coded in accordance to randomisation.

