## **5. Randomisation**

Patients will be randomised on entering the operating theatre. The anaesthetist responsible for the patient will open an envelope in which the group will be noted. Each patient will have an inclusion number and each inclusion number will correspond to attribution to a treatment group in accordance with a randomization list pre-established by the envelope technique. The envelopes will be created from 2 random lists.

Patients will be randomised to

- Flow I
- Conventional anaesthetic machine

for maintenance of anaesthesia.

and subsequently to a fresh gas flow of

- 1 L/min FiO2 0.5 oxygen in air

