## 6. Anaesthesia Protocol

All patients will follow the routines of the department expect for the randomisation of anaesthetic machine

All patients will receive general anaesthesia in accordance to local practice expect for the randomisation of anaesthetic machine and maintenance of a fresh gas flow of 1 L/min during anaesthesia.

- Establishment of intravenous access, 1000 ml Ringeractetat.
- All patients will have preoxygenation FiO2 0.8 for 60 seconds including 3 “deep breath” prior to propofol (2.5 mg/kg) fentanyl (2 microgr/kg) co-induction will be administered until adequately anaesthetised.
- Intravenous continuous infusion remifentanil will be administered in a dose 3 µg/ml
- Muscle relaxation will be administer in accordance to local practice
- Patients will be ventilated with oxygen for 3 minutes and thereafter intubated.

No surgery will commence until a 1.5 MAC is reached.

The vaporizer will be weighed before and after each patient anaesthetised and gram inhaled anaesthesia per minute anaesthesia will be calculated

The fresh gas flow is increased to 4 L/min oxygen and 2 L/min air when last stitch is made.

- Time to extubation
- Time to state name and date of birth
- Time to discharge from the PACU

All patients will receive PONV prophylaxis in accordance to local routines.

- PONV during the first 24 hours after surgery
- Patients satisfaction

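### The Objective describes three centres, each with its own standard comparator machine, but the primary g/min test ignores centre: a modest precision issue, and a question of which effect is estimated

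*Combined protocol and SAP*

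**What the plan says.** The Objective sets Flow-I against "the standard anaesthesia equipment/machine at the centre (multi-centre study; 3 centres"), and describes the comparator as a conventional machine with a bellows-reservoir circle. The Protocol Summary names one institution, "Department of Anaesthesia & Intensive Care Danderyds University Hospital".

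Practice is largely local. Section 6 gives anaesthesia "in accordance to local practice expect for the randomisation of anaesthetic machine and maintenance of a fresh gas flow of 1 L/min during anaesthesia", and adds "Muscle relaxation will be administer in accordance to local practice". Section 7 leaves the gas setting to clinical need once 1.5 MAC has been reached.

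Section 7 makes anaesthetic vaporised per minute the primary variable. The only tests, in section 8 under Power calculation, are Student's t-test and, for non-normal variables, the Wilcoxon test. Centre appears in neither.

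On allocation, section 5 says "The envelopes will be created from 2 random lists" without saying what the lists separate.

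**The concern.** If three sites contribute patients, g/min may differ between them in two ways. The control machines may differ, or local practice may shift consumption in both arms. A two-sample test leaves such differences in the error term and lets the arms differ in centre mix by chance.

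Three things are at stake: some power, the correct error rate if the envelopes are in fact stratified by centre, and the meaning of a pooled difference if the comparator is not the same machine everywhere.

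**Working it through.** **Inputs.** From section 8: control mean 0.28 g/min, SD 0.07, difference 0.03, significance level 0.05 (taken as two-sided), 43 per group, 100 recruited. From the Objective: three centres. Assumed, because the documents are silent: near-equal centres, centre means at −x, 0, +x (outer centres 2x apart), and one unstratified 1:1 list.

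**Step 1: the plan's own figure.** The two-group formula n = 2[0.07(1.960 + 0.842)/0.03]² gives about 86 per group, and the exact t calculation gives 87. Without the factor 2 it gives 42.7, the plan's 43. Noncentral-t power is 50.2% at 43 per group and 56.4% at 50. The centre effects below are therefore measured from a base of about 50-56%, not 80%.

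**Step 2: cost of the term when centres are equal, 50 per group.**
- Noncentrality without centre: 0.03/(0.07 × √(2/50)) = 2.143.
- Chance imbalance: centre explains on average 2/99 of the variance of the arm indicator, so the noncentrality becomes 2.143 × √(1 − 2/99) = 2.121 on 96 df. Power is 55.6% against 56.4%.
- Simulation (80,000 trials): 56.3% without and 55.4% with centre, a loss of 0.9 point. At 43 per group the loss is also 0.9.
- With allocation balanced within centre, only the degrees of freedom are lost: about 0.02 point.

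**Step 3: break-even (total SD held at 0.07).**
- Both arms shifted: between-centre variance is 2x²/3. Setting (2x²/3)/0.0049 = 2/99 gives x = 0.0122, so outer centres about 0.025 apart.
- Control machines only: the additive term absorbs half of each shift, with variance x²/6. Setting (x²/6)/0.0049 = 2/99 gives x = 0.0244, about 0.05 apart.

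**Step 4: change in power from adding centre, 50 per group, total SD 0.07 (simulation, percentage points).**

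| Outer centres apart (g/min) | 0 | 0.02 | 0.04 | 0.06 | 0.08 | 0.10 |
|---|---|---|---|---|---|---|
| Both arms shifted | −0.9 | −0.2 | +1.6 | +4.8 | +9.9 | +17.3 |
| Control machines only | −0.9 | −0.8 | −0.3 | +0.4 | +1.4 | +3.0 |

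The last column is extreme: 0.10/0.28 = 36% of the control mean.

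**Step 5: the meaning of the SD.** Section 8 takes 0.07 from a pilot and does not say whether it includes between-centre variation. If 0.07 is the within-centre SD, then at 0.10 apart with both arms shifted the total SD is √(0.0049 + 2 × 0.05²/3) = 0.081. Power is then 44-45% without and about 55% with centre, a gain of 10-11 points. With control machines only it is 48.5% against 50.7%, about 2 points.

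**Step 6: type I error (total SD 0.07).**
- Unstratified list, both arms shifted: 5.0-5.1% for the plain t-test.
- Unstratified list, control machines only, 0.10 apart: about 4.0% for both analyses, so conservative.
- Per-centre blocked lists, both arms shifted, plain t-test: 3.7% at 0.06 apart and 1.7% at 0.10. With the centre term it stays at 4.8-5.1%.

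**Step 7: effect by centre.** With 86/6 ≈ 14.3 patients per arm per centre, the 95% half-width is 1.96 × 0.07 × √(2/14.3) ≈ 0.051 g/min, wider than the 0.03 sought. By-centre results can only be descriptive. As an illustration, assumed centre effects of 0, 0.03 and 0.06 give a pooled effect of 0.018 with a 60/20/20 patient mix and 0.042 with 20/20/60.

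**The case against.** The strongest case against acting is that the benefit is undocumented. No between-centre variance is given, and the comparators share a type, so different models are an inference. In the control-machine mechanism that the Objective's wording suggests, the term loses power up to about 0.05 g/min apart and gains about 3 points at most. The large gains need local practice to shift both arms strongly. Section 8 also calls the study an explorative pilot. All of this stands, and it is why the point ranks low. What survives is the asymmetry: at most about 1 point lost, against a larger gain if sites differ materially.

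A reader might infer more than the documents support:
- **That the planned test is biased or anticonservative.** Section 8 plans two equal groups and no section plans different ratios by centre. Chance imbalance then adds variance, not bias.
- **That the term always helps when centres differ.** Small real differences still cost power.
- **That only precision is affected.** Different control machines could change the treatment effect by centre, and then the question is which effect the pooled figure describes.
- **That the single institution contradicts three centres.** It may be the coordinating site, and a site list on the title pages, which are not in the text available here, cannot be ruled out.
- **That the two lists are a failed stratification.** They may be left over from a two-step allocation. Section 5 continues "and subsequently to a fresh gas flow of" with a single option, and the eligibility section still has care following routine "apart from the volatile anaesthetic and fresh-gas flow that the patient is randomised to".

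**Conclusion.** The point holds as a low-severity improvement, to consider rather than to require. If there are three centres, leaving centre out of the primary analysis can waste precision. Within the assumed range at 50 per group, the term moves power from about −0.9 point to about +17, and the upper end needs an extreme shift in both arms with total SD 0.07. If the envelopes are stratified by centre, the case is firmer: the term then costs almost nothing, and the plain t-test is conservative when centre shifts both arms. The additive term does not answer whether the machine effect is the same at every centre.

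These figures rest on near-equal centres and assumed shifts, and all but the stratified-list results on one unstratified 1:1 list. If there is only one centre, the statistical point falls away. The sample-size shortfall (about 50% power at 43 per group) is separate and much larger than the cost of the term.

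**What to change.** 1. Reconcile the Protocol Summary and the Objective on the number of centres. State in section 5 what the two lists separate, or delete the second if it is a remnant.
2. If there are three centres, pre-specify before any data are seen a linear model for g/min with arm and centre as fixed effects as the primary analysis. Use a centre-stratified rank test if the outcome is clearly non-normal.
3. Name the comparator machine at each centre, and report the arm difference by centre with confidence intervals, labelled descriptive.
4. Per-centre lists are optional. If used, they need the centre term in the analysis and randomly varied, undisclosed block sizes, because "The anaesthetist responsible for the patient will open an envelope in which the group will be noted" and the machine is visible.
5. If there is one centre, correct the Objective and keep the planned test.

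The cost is a few sentences, two degrees of freedom, and about 0.9 point of power if centres turn out equal under an unstratified list. Per-centre lists would add envelope sets and some risk of predictable allocation. None of this replaces correcting the sample size.

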### **3. Inclusion and Exclusion Criteria**

100 ASA 1-2 patients aged 20 – 60 years scheduled for elective general anaesthesia will be recruited.

#### **Inclusion criteria**

- Age 20 to 60 years
- BMI 20-30
- ASA 1-2

#### **Exclusion criteria**

- COPD
- BMI > 30
- ASA >2
- Severe cardiovascular disease ASA >2
- Renal disease
- Diabetes
- Hepatic disease
- Psychiatric disease or any psychoactive medication

All patients will receive all treatment and care in accordance to the routines of the department apart from the volatile anaesthetic and fresh-gas flow that the patient is randomised to.

All study specific data will be recorded and collected on a Case Record Form coded in accordance to randomisation.

#### **4. Ethics Committee Approval and Patient Informed Consent**

The study will be reviewed by regional Ethics Review Board. The protocol will be reviewed by registered in Clinical Trial Data bases in accordance to National Regulations

The study will not be initiated before approval has been received from the Ethics Review Board and reviewed by National drug authority as needed.

All patients will receive verbal and written information and signed informed consent will be required before any patients are entered into the study.

## **5. Randomisation**

Patients will be randomised on entering the operating theatre. The anaesthetist responsible for the patient will open an envelope in which the group will be noted. Each patient will have an inclusion number and each inclusion number will correspond to attribution to a treatment group in accordance with a randomization list pre-established by the envelope technique. The envelopes will be created from 2 random lists.

Patients will be randomised to

- Flow I
- Conventional anaesthetic machine

for maintenance of anaesthesia.

and subsequently to a fresh gas flow of

- 1 L/min FiO2 0.5 oxygen in air

## 6. Anaesthesia Protocol

All patients will follow the routines of the department expect for the randomisation of anaesthetic machine

All patients will receive general anaesthesia in accordance to local practice expect for the randomisation of anaesthetic machine and maintenance of a fresh gas flow of 1 L/min during anaesthesia.

- Establishment of intravenous access, 1000 ml Ringeractetat.
- All patients will have preoxygenation FiO2 0.8 for 60 seconds including 3 “deep breath” prior to propofol (2.5 mg/kg) fentanyl (2 microgr/kg) co-induction will be administered until adequately anaesthetised.
- Intravenous continuous infusion remifentanil will be administered in a dose 3 µg/ml
- Muscle relaxation will be administer in accordance to local practice
- Patients will be ventilated with oxygen for 3 minutes and thereafter intubated.

No surgery will commence until a 1.5 MAC is reached.

The vaporizer will be weighed before and after each patient anaesthetised and gram inhaled anaesthesia per minute anaesthesia will be calculated

The fresh gas flow is increased to 4 L/min oxygen and 2 L/min air when last stitch is made.

- Time to extubation
- Time to state name and date of birth
- Time to discharge from the PACU

All patients will receive PONV prophylaxis in accordance to local routines.

- PONV during the first 24 hours after surgery
- Patients satisfaction

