## **10. Insurance**

All treatments except randomisation will be given in accordance to the routines of the department. No extra insurance is therefore required. The National Patient Safety Insurance will cover potential insurance claims.

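### Does giving the remifentanil dose in µg/ml, a concentration unit, call for a change to the plan?

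*Combined protocol and SAP*

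**What the plan says.** The drug list in Section 6 contains one line on remifentanil: "Intravenous continuous infusion remifentanil will be administered in a dose 3 µg/ml". The bullet above it gives the induction drugs by body weight: "propofol (2.5 mg/kg) fentanyl (2 microgr/kg) co-induction will be administered until adequately anaesthetised". The bullet below it leaves muscle relaxation to each site's own practice and prints no figure.

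Four general statements surround these bullets. Section 6 opens with two: "All patients will follow the routines of the department expect for the randomisation of anaesthetic machine", and "All patients will receive general anaesthesia in accordance to local practice expect for the randomisation of anaesthetic machine", the second also excepting the 1 L/min fresh gas flow. The text under Exclusion criteria in Section 3 says "All patients will receive all treatment and care in accordance to the routines of the department apart from the volatile anaesthetic and fresh-gas flow". Section 10 (Insurance) says "All treatments except randomisation will be given in accordance to the routines of the department". None of the four lists remifentanil among its exceptions. The Objective section describes a "multi-centre study; 3 centres".

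The primary variable in Section 7 is the amount of inhaled agent vaporised per minute of anaesthesia.

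**The concern.** The word for a dose is attached to a unit of concentration. The neighbouring drugs have figures from which an amount follows once body weight is known; remifentanil does not. A reader can take 3 µg/ml as the strength of the prepared solution or as a target concentration, and these are different instructions. The line also prints a figure where the next bullet simply defers to local practice, so it is unclear whether the figure binds the centres or yields to their routine.

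Two things could be at stake. One is safety, since this is an opioid instruction that three centres might interpret differently. The other is the primary comparison. Section 7 lets the gas setting follow clinical need once 1.5 MAC has been reached, so differences in accompanying drugs could in principle add variability to agent consumption.

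**Working it through.** No figure in the plan has to be reproduced, and the point involves no significance level, power, effect size or sample size. The check is one of units, followed by a reading of the related text.

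**Units in the Section 6 list**

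| Drug | Figure | To obtain an amount | Derivable from the line? |
|---|---|---|---|
| Propofol | 2.5 mg/kg | 2.5 mg/kg × weight in kg = mg | Yes, nominally |
| Fentanyl | 2 µg/kg | 2 µg/kg × weight in kg = µg | Yes, nominally |
| Remifentanil, as solution strength | 3 µg/ml | 3 µg/ml × *V* ml = 3*V* µg | No, *V* is not stated |
| Remifentanil, as target concentration | 3 µg/ml | Does not follow from the figure alone | No |

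Two of the three drugs with a figure are in mass per kg and one is in mass per volume. That contrast is weak evidence of error. Propofol and fentanyl are given at induction until the patient is adequately anaesthetised, while remifentanil runs continuously, and different modes of administration can use different units. What stands is the mismatch between the word and the unit.

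**Whether other text resolves the figure.** It does not. The protocol has no other mention of remifentanil, and no infusion rate, dilution, target-controlled mode or plasma or effect-site target.

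**Whether the line can be carried out.** Under both readings µg/ml is a legitimate unit, so the line is incomplete but not shown to be wrong. If it is taken as a solution strength, the missing rate and titration fall to the local practice that Section 6 invokes twice. The absence of remifentanil from the listed exceptions supports this: on their face the general statements leave its conduct with the department. Section 5 also places an anaesthetist in charge of each patient. This shows only that the line is workable, not which reading was intended. The Section 10 sentence explains why no extra insurance is needed and carries little weight as an anaesthetic instruction.

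**Whether the trial's result depends on it.**

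- *Between arms:* patients are randomised to the machine, and the remifentanil line is the same for both groups. The ambiguity gives no mechanism that favours one machine.
- *Precision:* if the three centres read the line differently, agent consumption might vary more. The documents contain nothing from which to size this. Section 8 takes an SD of 0.07 g/min from pilot experience and does not say how remifentanil was given there, so no inflation can be calculated.
- *Analysis:* the Section 8 comparisons (Student's t-test or Wilcoxon test) do not use the remifentanil figure.

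**The case for a change.** The strongest case for acting is that an opioid instruction should have one meaning, and that correcting it costs one line. Deferring to local practice does not explain what a printed number denotes. The protocol defers expressly where it means to, for muscle relaxation and for antiemetic prophylaxis, so a printed figure can fairly be taken as binding. Read literally, local routine governs the drug while Section 6 also fixes a number for it, and the text does not say which prevails. Adherence to the line therefore cannot be checked.

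All of that stands as a description of the text. It supports a request to the investigator to reconcile the word, the unit and the local-practice statements in Sections 3 and 6. It does not establish a consequence. No wrong amount is shown to follow, no arm is favoured, and the possible extra variability between centres has no size that the documents support. Adherence to this line is also not an outcome and enters no analysis described in Sections 7 and 8.

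**Conclusion.** The ambiguity is genuine, but no change to the plan follows. It amounts to one line, the drug's only mention, with two possible readings. No effect on the primary variable, on the comparison between machines or on the amount actually given can be shown. Clearing up the wording would leave the design, the data collected and the analysis as they are.

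This rests on two assumptions. The first is that the general statements in Sections 3 and 6 mean what they say, so that departments conduct the infusion under their own routine. The second is that the line is applied alike in both arms, as it is written. Which reading was intended is for the investigator to state as an editorial clarification, and nothing here takes a view on it.

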## **7. Outcome Variables**

**Primary study variable**, amount of gas vaporized halogenated anaesthetic per minute anaesthesia.

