### **Secondary study variables;**

1. Time needed to increase from Etaa 1 to Etaa 1.5 age adjusted MAC with a constant 1 L/min. and a dialled 3 MAC, the vaporiser set at 18 %, in conjunction to start of surgery
  - a. When the 1.5 Etaa has been achieved the gas setting should be adjusted in accordance to clinical needs throughout the surgery.
2. Time needed during wash-out, time from cessation of administration until reaching 0.2 MAC
  - a. Time from cessation of administration to awakening; extubation and able to state name and date of birth
  - a. Time to reach Aldrete > 8
  - b. Pain and need for analgesics and anti-emetics during the PACU stay
  - c. Follow-up of quality of recovery PQRS

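### Does the undefined clock behind grams per minute make the primary outcome understate a saving made during wash-in?

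*Combined protocol and SAP*

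**What the plan says.** The primary variable in Section 7 (Outcome Variables) is the "amount of gas vaporized halogenated anaesthetic per minute anaesthesia". The Main measurements in Section 1 say "Gram inhaled anaesthetic per minute anaesthesia", and Section 6 (Anaesthesia Protocol) describes the measurement: "The vaporizer will be weighed before and after each patient anaesthetised and gram inhaled anaesthesia per minute anaesthesia will be calculated". The numerator is therefore all agent used in the case, wash-in included. None of these places gives a start or stop event for the minutes. The power calculation in Section 8 does not say which clock produced its pilot value of 0.28 g/min.

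Three other statements bear on the point.

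- **Hypothesis.** The Objective says that Flow-I "provides a faster and less anaesthetic vapour consuming wash-in and maintenance". Section 1 says it "provides a faster and less gas consuming equilibrium and maintenance of general anaesthesia".
- **The timed step.** Secondary variable 1 times the rise from 1 to 1.5 MAC at 1 L/min with "a dialled 3 MAC, the vaporiser set at 18 %, in conjunction to start of surgery". Afterwards "the gas setting should be adjusted in accordance to clinical needs throughout the surgery".
- **Start of surgery.** Section 6 states: "No surgery will commence until a 1.5 MAC is reached".

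**The concern.** Read together, these statements suggest that the denominator may carry part of the treatment effect. If Flow-I reaches 1.5 MAC sooner and surgery then starts sooner, the Flow-I patient has fewer grams and also fewer minutes. Dial and flow are the same in both arms during the step, so a saving there could come from time and not from a lower rate. Numerator and denominator would fall together, and the ratio would show less than the saving per patient. Using one clock for everyone would not remove this if that clock includes wash-in.

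The Objective names vapour consumption and associated cost, so agent saved in wash-in belongs to the aim. A discounted saving would be reported as too small and would be harder to detect. An unstated clock also leaves room for different centres to time differently, or for a choice after the data are seen. The worst case, picking among four clocks after unblinding, was put at a type I error of about 6 to 8%.

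**Working it through.** **Inputs from the protocol.** Control mean R = 0.28 g/min, SD 0.07, planned reduction 0.03 g/min, 43 per group (Section 8); vaporiser at 18% and 1 L/min during the step (Section 7).

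**Assumptions, not in the protocol.** One litre of desflurane vapour weighs 7.0 g (range 6.8 to 7.5). Case lengths, step times and minutes saved are also assumed.

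**1. The plan's own figures.** The planned effect is 0.03/0.28 = 10.7%, stated on the outcome's own scale. For two groups, n = 2 × (1.96 + 0.84)² × 0.07²/0.03² gives 86 per arm, not 43; power at 43 per arm is 51%. That mismatch is a separate matter and does not depend on the clock. Power below is at 43 per arm.

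**2. The algebra.** Let T be the minutes, s the minutes saved in wash-in and r the wash-in rate.

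- On unchanged minutes the reduction is r·s/T.
- On a clock that includes wash-in it is R − (R·T − r·s)/(T − s) = s(r − R)/(T − s).
- The fraction shown is (1 − R/r) × T/(T − s).

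**3. Wash-in rate.** 0.18 × 7.0 = 1.26 g/min if 1 L/min is total flow; (0.18/0.82) × 7.0 = 1.54 g/min if it is carrier flow. Over 6.8 to 7.5 g/L the range is 1.22 to 1.65 g/min.

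**4. Whole saving from wash-in minutes.** Set r·s/T = 0.030. With r = 1.26, s/T = 0.0238, the Flow-I value is 0.25/(1 − 0.0238) = 0.2561, and the reduction reads 0.0239. With r = 1.54 it reads 0.0250; the ends of the range give 0.0237 and 0.0254. So 15 to 21% is lost, whatever the case length.

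**5. Half from wash-in minutes.** s/T = 0.015/r, and the reduction reads 0.0269 to 0.0277 (8 to 10% lost).

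**6. None from wash-in minutes.** It reads 0.030.

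A lower wash-in rate would lose more. At three times the mean (0.84 g/min), with 2 minutes saved out of 60, 69% of the saving shows. The 18% setting implies about 4.4 to 5.9 times the mean (1.22/0.28 to 1.65/0.28).

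**7. Power when all the saving is wash-in time** (simulated, no variation in vaporiser time before the step):

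| Median surgery, minutes saved | Fall in grams per patient | Fall in g/min | Power, g/min | Power, grams adjusted for surgery minutes |
|---|---|---|---|---|
| 30 min, 1 | 13.4% | 11.3% | 60% | 76% |
| 60 min, 2 | 13.6% | 12.0% | 72% | 82% |
| 120 min, 2 | 6.9% | 6.2% | 27% | 32% |

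If 1.5 MAC limits only half of surgery starts, the pairs are 63 vs 69, 72 vs 74 and 26 vs 26. If the saving is in maintenance only, they are 43 vs 46, 51 vs 51 and 56 vs 56. With no effect, rejection is 4.7 to 4.8% for g/min and 5.0 to 5.5% for adjusted grams.

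**8. Power when vaporiser time before the step varies.** All the saving is still wash-in time. The added period runs at 0.42 g/min with log-SD 0.5 (both assumed).

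| Median time before step | 30 min surgery, g/min vs adjusted grams | 60 min surgery, g/min vs adjusted grams |
|---|---|---|
| 8 min | 50 vs 52 | 66 vs 73 |
| 15 min | 41 vs 28 | 60 vs 56 |
| 20 min | 34 vs 20 | 55 vs 45 |

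Surgery minutes do not capture agent used before the step; grams per minute normalises for it. The alternative's advantage shrinks and then reverses.

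**The case for a change.** The strongest case for a change is this. The omission is plain, and the dilution follows from an identity: the ratio of grams per minute equals the ratio of grams multiplied by conventional minutes over Flow-I minutes. The protocol itself supplies the hypothesis of faster wash-in and the rule that surgery waits. Naming a start and stop event would cost a sentence or two, and the weights for a comparison of total grams are already planned.

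The omission and the identity stand. The step from them to a flawed primary outcome does not, for four reasons.

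- **The rule is a floor, not a trigger.** Section 6 bars surgery before 1.5 MAC; it does not say that surgery begins once 1.5 MAC is reached. If preparation of the patient sets the start, a faster step leaves the minutes unchanged and grams per minute shows the full saving.
- **The saving need not be minutes.** Section 8 attributes the expected 0.03 g/min to the way Flow-I injects vapour, and the background notes that machines differ in fresh gas delivery. An equal dial setting does not establish equal grams per minute on two machines. A rate saving is not diluted.
- **The planned 0.03 is already in grams per minute.** Treating it as a saving on unchanged minutes and then shrinking it is a reinterpretation. In two of the three wash-in simulations the fall in grams per minute (11.3% and 12.0%) exceeds the planned 10.7%. Power is lower only against a different estimand.
- **Wash-in is not hidden.** Its vapour is in the weighed grams, and its duration is a main measurement and secondary variable 1.

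**Conclusion.** This is missing detail that analysts would fill sensibly, with one clock for every patient. Vaporiser-on to cessation is an obvious candidate, and secondary variable 2 already needs the cessation time. Following the plan that way gives a sound comparison of grams per minute: the direction of effect is kept and type I error stays near 5%. The 6 to 8% figure requires choosing the clock after unblinding, which nothing in the protocol suggests.

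Under the assumed vapour density and the 18% delivery rate, at most about 15 to 21% of the saving goes unseen. That requires the whole saving to be wash-in time and 1.5 MAC to set the start of surgery. It falls to 8 to 10% if half the saving is wash-in time, and to nothing if the saving is a delivery rate or surgery waits for other reasons. The protocol gives no durations or wash-in rates that would settle which case applies. The unstated pilot clock affects how well 0.28 g/min carries over to planning, not the validity of the comparison between arms.

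Total grams adjusted for surgery minutes would be a change of estimand with mixed returns: it gains power when time before the step is constant and loses it when that time is long and variable. Choosing grams per minute is a fair trade-off, and no change to the plan follows.
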